## 12.6.2 Injection Site Reactions

### 12.6.2.1 Investigator Assessment

On the days of the vaccination, injection site tolerability will be assessed by the Investigator up to a minimum of 4 hours after the first injection and approximately 24 hours and 7 days after the first injection. For subsequent injections, injection site tolerability will be assessed by the Investigator up to 2 hours on the day of injection by the study site.

Investigator assessed injection site reactions will be graded according to [Table 3](#) below:

Table 3: Grading for investigator assessed injection site tolerability					
	Grade 0	Grade 1	Grade 2	Grade 3	Grade 4
Erythema/redness	0-2.4 cm	2.5-5 cm	5.1-10 cm	>10 cm	Necrosis or exfoliative
Swelling	0-2.4 cm	2.5-5 cm and does not interfere with activity	5.1-10 cm or interferes with activity	>10 cm or prevents daily activity	Necrosis
Induration/hardening	0-2.4 cm	2.5-5 cm and does not interfere with activity	5.1-10 cm or interferes with activity	>10 cm or prevents daily activity	Necrosis
Pain/tenderness (Pain on pressure)	Absent	Mild discomfort to touch	Discomfort with movement	Significant discomfort at rest	Emergency room visit or hospitalisation
Pain (spontaneous; pain without pressure)	Absent	Does not interfere with activity	Repeated use of non-opioid pain reliever >24 hours or interferes with activity	Any use of opioid pain reliever or prevents daily activity	Emergency room visit or hospitalisation
Pruritis/itching	Absent	Mild	Moderate	Severe	Not applicable
Wheal(s)	0-2.4 cm	2.5-5 cm	5.1-10 cm	>10cm	Not applicable
Burning sensation	Absent	Mild	Moderate	Severe	Not applicable

For the Day 85 analysis the following investigator assessed summaries will be presented for the Safety Analysis Set by treatment group:

- The number and percentage of subjects with any injection site reactions by type, and any severe reactions by type
- The number and percentage of subjects with injection site reactions will be summarised by maximum severity at any time point and for each study time point.

For the Day 225 analysis the following investigator assessed summary will be presented for the Safety Analysis Set by treatment group:

- The number and percentage of subjects with injection site reactions by severity and time point.

Severe injection site reactions are those assigned a grade 3 or 4 from the above table.

Individual injection site reaction examination results will be listed. In addition, any injection site reactions that are considered by the investigator to be adverse will be recorded as an AE in the eCRF. Any injection site reaction that meets the criteria of serious will be reported as an SAE.

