3.3 Outcome measures/endpoints

3.3.1 Primary endpoints/outcomes

- Solicited AEs related to injection site tolerability during the week following each vaccine administration
- Unsolicited AEs through day 85

- Serious adverse events (SAEs) and AEs of special interest (AESIs) through 6 months after last vaccine dose
- Vital signs
- ECG
- Safety Laboratory including laboratory assessment of liver inflammation and function

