## 7.0 Study Variables and Covariates

### 7.1 Primary Variables

- Solicited adverse events (AEs) related to injection site tolerability during the week following each vaccine administration.
- Unsolicited AEs through day 85
- Serious adverse events (SAEs) and AEs of special interest (AESIs) through 6 months after last vaccine dose
- Vital signs
- ECGs
- Safety laboratory assessments including laboratory assessment of liver inflammation and function

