#### 12.6.1 Adverse Events

Adverse events will be coded using Version 20.0 or newer of MedDRA.

Treatment-emergent adverse events (TEAEs) are those which first occur or increase in severity or relationship probability to investigational product after the first dose of investigational product through 30 days after last dose of investigational product. Note that SAEs and AESIs are collected through 6 months after last dose of investigational product; therefore, all SAEs and AESIs will be summarized, not just treatment-emergent events.

All AEs which change in severity or relationship to investigational product are assigned a new start date and captured as a new record.

If more than 1 AE with the same preferred term is reported before the date of the dose of investigational product, then the AE with the greatest severity will be used as the benchmark for comparison to the AEs occurring during the study under the preferred term.

An overall summary of TEAEs, including the number and percentage of subjects who experience, and absolute count of treatment-emergent events for:

- Any TEAE
- Any TEAE by maximum severity
- Any TEAE considered possibly related to investigational product (defined as CRF response of "Reasonable Possibility")
- Any TEAE considered possibly related to investigational product by maximum severity
- Any SAEs
- Any SAEs considered possibly related to investigational product
- Any AEs with outcome of death
- Any AESIs (Hepatic flares and autoimmune conditions)
- Any TEAE leading to discontinuation of investigational product

The number and percentage of subjects reporting TEAEs, SAEs, or AESIs will be tabulated in the following ways by treatment group.

- By SOC and preferred term (including absolute count of events).
- By SOC, preferred term and maximum severity.
- By SOC and preferred term for TEAEs possibly related to investigational product in the opinion of the investigator (including absolute count of events).
- By SOC and preferred term for SAEs (including absolute count of events).
- By SOC and preferred term for possibly related SAEs (including absolute count of events).
- By SOC and preferred term for TEAEs leading to discontinuation of investigational product (including absolute count of events).
- By SOC and preferred term for AEs with fatal outcome (including absolute count of events).
- By SOC and preferred term for AESIs (including absolute count of events).

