Table 14.2.2.2	Qualitative Virology Results by Time Point - HBsAb	Immunogenicity Analysis Set	
Table 14.2.2.3	Quantitative Virology Results by Time Point - HBsAg and HBV DNA	Full Analysis Set	X
Table 14.2.2.4	Qualitative Virology Results by Time Point - HBsAb	Full Analysis Set	
Figure 14.2.2.5	Line Plot of Change from Baseline in log10 HBsAg at each Timepoint by Treatment Group	Immunogenicity Analysis Set	
Figure 14.2.2.6	Line Plot of Change from Baseline in log10 HBsAg at each Timepoint by Treatment Group	Full Analysis Set	
Table 14.3.1.1	Summary of Investigational Product Exposure	Safety Analysis Set	
Table 14.3.2.1	Overall Summary of Adverse Events	Safety Analysis Set	
Table 14.3.2.2	Treatment-emergent Adverse Events by System Organ Class and Preferred Term	Safety Analysis Set	X
Table 14.3.2.3	Treatment-emergent Adverse Events by System Organ Class and Maximum Severity	Safety Analysis Set	
Table 14.3.2.4	Serious Adverse Events by System Organ Class and Preferred Term	Safety Analysis Set	
Table 14.3.2.5	Possibly Treatment-Related Treatment-emergent Adverse Events by System Organ Class and Preferred Term	Safety Analysis Set	
Table 14.3.2.6	Serious Possibly Treatment-Related Adverse Events by System Organ Class and Preferred Term	Safety Analysis Set	
Table 14.3.2.7	Possibly Treatment-Related Treatment-emergent Adverse Events by System Organ Class and Maximum Severity	Safety Analysis Set	
Table 14.3.2.8	Treatment-emergent Adverse Events leading to Discontinuation of Investigational Product by System Organ Class and Preferred Term	Safety Analysis Set	
Table 14.3.2.9	Adverse Events with Fatal Outcome by System Organ Class and Preferred Term	Safety Analysis Set	
Table 14.3.2.10	Adverse Events of Special Interest by System Organ Class and Preferred Term	Safety Analysis Set	
Table 14.3.3.1.1	Haematology Results by Time Point	Safety Analysis Set	
Table 14.3.3.1.2	Investigator Assessed Clinically Significant Postbaseline Haematology Results	Safety Analysis Set	
Table 14.3.3.1.3	Shift Summary of Haematology Results by Reference Range and Time Point	Safety Analysis Set	

Table 14.3.3.2.1	Biochemistry Results by Time Point	Safety Analysis Set	
Table 14.3.3.2.2	Investigator Assessed Clinically Significant Postbaseline Biochemistry Results	Safety Analysis Set	
Table 14.3.3.2.3	Shift Summary of Biochemistry Results by Reference Range and Time Point	Safety Analysis Set	X
Table 14.3.3.3.1	Quantitative Urinalysis Results by Time Point	Safety Analysis Set	

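### No planned summary table reports the primary variable of unsolicited AEs to Day 85: the AE tables pool in local reactions judged adverse and use a window that can end earlier

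*SAP*

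**What the plan says.** The protocol and SAP separate two kinds of event. Protocol 3.3.1 lists "Solicited AEs related to injection site tolerability during the week following each vaccine administration", and SAP 7.1 repeats it almost word for word. The next item in both lists is "Unsolicited AEs through day 85".

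The analysis section does not carry the split forward. SAP 12.6.1 defines TEAEs as events that first occur, or worsen in severity or relationship, "after the first dose of investigational product through 30 days after last dose of investigational product". It plans "An overall summary of TEAEs, including the number and percentage of subjects who experience" each category of event, and then states: "The number and percentage of subjects reporting TEAEs, SAEs, or AESIs will be tabulated in the following ways by treatment group". None of the tabulations that follow is restricted to unsolicited events. In Appendix 1 the main AE table is titled "Treatment-emergent Adverse Events by System Organ Class and Preferred Term", and no title from Table 14.3.2.1 to Table 14.3.2.10 mentions unsolicited events.

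Local reactions have their own outputs, Tables 14.3.6.1 to 14.3.6.5. SAP 12.6.2.1 also gives them a route to the AE page: "any injection site reactions that are considered by the investigator to be adverse will be recorded as an AE in the eCRF". It states no criterion for adverse and no exclusion for reactions within the solicited week.

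SAP 4.1, which lists changes from the protocol, covers physical examinations and the Immunogenicity Analysis Set. It does not mention the unsolicited-AE variable.

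**The concern.** If the plan is followed exactly, one of the trial's named primary variables has no summary. The TEAE tables are the nearest substitute, but they differ from it in content and in time. They can include solicited local reactions, depending on each investigator's judgement, and their window is tied to the last dose rather than to Day 85.

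The primary analysis is meant to inform the design of the next study and to confirm formulation and dose (Protocol 10.11, SAP 10.2). For that purpose it helps to know whether a difference between arms in overall AE rates comes from local reactogenicity, which is already tabulated elsewhere, or from other events. The planned tables do not let a reader make that separation for individual subjects.

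**Working it through.** The plan gives no figure for this point, so there is none to reproduce. The check has three parts.

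**1. Tracing the variable from definition to output**

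| Step | Solicited local reactions | Unsolicited AEs |
|---|---|---|
| Named as primary (Protocol 3.3.1, SAP 7.1) | yes, week after each injection | yes, through Day 85 |
| Collection | investigator form and diary card (SAP 12.6.2); also the AE page if judged adverse | AE page, by non-directive questioning (Protocol 9.2) |
| Summary table | 14.3.6.1 to 14.3.6.5 | none specific; contained in the TEAE tables |
| Listing | 16.2.11.1 and 16.2.11.2 | 16.2.7.1, all AEs, no flag specified |

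A new local reaction after dose 1 that is entered on the AE page meets the TEAE definition. It is then counted in Tables 14.3.2.x and also in Tables 14.3.6.x.

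**2. Whether the unsolicited rate can be recovered from the tables**

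Within one arm and one common time window, let T be the number of subjects with any TEAE, L the number with at least one local reaction on the AE page, and U the number with at least one unsolicited AE. The tables imply only T − L ≤ U ≤ T.

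The following rates are assumed and do not come from the documents. Take 10 subjects, an unsolicited rate of 40%, local reactions entered as AEs in 50%, and independence. The expected any-TEAE rate is 1 − (0.60 × 0.50) = 0.70, so T = 7 and L = 10 × 0.50 = 5. A reader holding T and L could conclude only that U lies between 7 − 5 = 2 and 7. The value that generated the numbers was 4. L itself is not printed either, because local terms fall in separate rows and one subject may appear in several. The same applies to the related and maximum-severity rows. A preferred term alone also cannot distinguish a reaction within 7 days of an injection from a later one, which would be unsolicited.

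Under the same formula, the any-TEAE rate exceeds the unsolicited rate u by (1 − u) × r, where r is the share of subjects with a local reaction entered as an AE. For u from 20% to 60% and r from 10% to 80%, this runs from 0.40 × 0.10 = 0.04 to 0.80 × 0.80 = 0.64, or 0.4 to 6.4 subjects per 10. The width of that range reflects the lack of any input from the documents and is not an estimate.

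**3. The time window**

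The window ends 30 days after the last dose. On the nominal schedule:

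| Last dose | TEAE window ends | Days short of Day 85 |
|---|---|---|
| Day 57 | 57 + 30 = Day 87 | 0 |
| Day 29 | 29 + 30 = Day 59 | 85 − 59 = 26 |
| Day 1 | 1 + 30 = Day 31 | 85 − 31 = 54 |

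Protocol 7.10 encourages subjects who stop treatment to stay in follow-up, and Protocol 9.2 has all AEs recorded to Day 85. Anyone with at least one injection is in the Safety Analysis Set. Non-serious, non-AESI events arising in these gaps are therefore recorded and listed but fall outside the TEAE tables.

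**The case against.** The case for the plan as written has real force.

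- **The TEAE tables do what the protocol asks.** Protocol 10.9.2 calls for tabulation of all treatment-emergent AEs. A local reaction judged adverse is an AE under Protocol 9.1, and the endpoint list itself calls local reactions solicited AEs. Counting such a reaction in both table series is not double counting within one rate. This stands, and it rules out replacing the TEAE tables. Restricting them to unsolicited events could also remove a non-serious local reaction from the relatedness rows, or from the discontinuation rows if it ended dosing.
- **Most of the information is present.** Unsolicited TEAEs appear by preferred term with event counts, and all AEs are listed. Appendix 1 marks Table 14.3.2.2 and the diary table 14.3.6.3 as top-line, so readers see TEAEs by term alongside local reactions. This stands too. What is missing is the subject-level summary and the period after the TEAE window closes.
- **No formal decision depends on it.** SAP 12.0 plans no hypothesis testing, and SAP 10.1 has the Safety Review Committee work from listings. This limits the importance of the point but does not supply the variable.

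Two stronger readings are tempting. A reader might infer that the variable is missing because local reactions contaminate the TEAE tables. That mixing is only part of the cause: no unsolicited output is specified at all, and the window would be wrong for early stoppers even if no local reaction reached the AE page. A reader might also infer a large artificial difference between arms driven by recording habit. The documents give neither local-reaction rates nor the share that would be judged adverse. Protocol 7.4 keeps those who prepare or give injections apart from clinical assessments. If local reactions do differ between arms, the resulting TEAE difference is a genuine treatment effect, though not one in unsolicited events.

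**Conclusion.** The point holds as a gap between a stated primary variable and the planned outputs. No summary table gives unsolicited AEs through Day 85, and the any, related and maximum-severity rates at subject level cannot be derived from the tables that are planned.

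The time shortfall follows directly from the nominal schedule: 26 days after a last dose on Day 29 and 54 days after a last dose on Day 1. It applies only to subjects who stop early, and the documents do not say how many to expect. The overlap between solicited and unsolicited events has no supportable size. The figures in part 2 of the working show only why the rate is not recoverable.

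The gap begins in the protocol, since section 10.9.2 also asks only for TEAE tables. It does not invalidate those tables or affect any error rate. It is worth closing because the trial would otherwise not summarise a variable that it calls primary.

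**What to change.** Add to SAP 12.6.1 and Appendix 1, and replace nothing:

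1. Derive a solicited flag for each AE record: yes if the term matches a reaction in SAP Table 3 or Table 4 and onset is within 7 days after an injection, otherwise no. Agree the term list at the blinded data review meeting already planned in SAP 11.3.
2. Show the flag in Listing 16.2.7.1.
3. Add rows to Table 14.3.2.1 for any unsolicited AE, any related unsolicited AE, and unsolicited AEs by maximum severity.
4. Add one table of unsolicited AEs by system organ class and preferred term, covering first dose through Day 85 whatever the date of last dose. Use the same period for the new rows in Table 14.3.2.1.
5. Leave all existing TEAE, relatedness, discontinuation and SAE tables as they are, in line with Protocol 10.9.2.

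The cost is one derived variable, a few rows, one extra table and a short term list to agree while blinded. The data are already being collected. The overall summary would then carry two periods, so its footnote should state both.

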#### 12.6.2.2 Patient-reported Diary Cards

Additionally, a diary card will be provided to the subjects to record injection site reactions from 4 hours (first injection) or 2 hours (subsequent injections) post injection to 7 days post injection. Data from the diary card will be transcribed into the appropriate eCRF page as below:

**Table 4: Grading for subject diary-assessed injection site tolerability**

Size of the reaction (please measure the longest dimension or longest side):		Discomfort of the reaction:			
Reaction	Present?	If yes, how bad was the reaction?			
		Grade 0	Grade 1	Grade 2	Grade 3
Redness	Yes/No	Small	Medium	Large	Very large
Swelling	Yes/No	Small	Medium and mild	Large or moderate	Very large or very bad
Hardening	Yes/No	Small	Medium and mild	Large or moderate	Very large or very bad
Pain on touch	Yes/No	Absent	Mild	Moderate	Very bad
Pain without touch	Yes/No	Absent	Mild	Moderate	Very bad
Itching	Yes/No	Absent	Mild	Moderate	Very bad
Burning	Yes/No	Absent	Mild	Moderate	Very bad
Lump	Yes/No	Small	Medium	Large	Very large

Severe injection site reactions from the diary card data are those reported as either 'Very large' in the case of size-based reactions (redness, swelling etc.) or 'Very bad' in terms of pain-based reactions (pain on touch, itching etc.).

For the Day 85 analysis the following diary assessed summary will be presented for the Safety Analysis Set by treatment group:

- The number and percentage of subjects with any injection site reactions recorded on the diary card by type, and any severe reactions by type, and most recent injection number.

For the Day 225 analysis the following diary assessed summary will be presented for the Safety Analysis Set by treatment group:

- The number and percentage of subjects with injection site reactions by severity and time point.

The categories on the table are chosen to follow closely the choices in the investigator assessment and will be displayed as follows:

Table 5: Diary card to CSR table mapping of injection site reaction terms	
Diary Card	Table
Redness	Erythema/redness
Swelling	Swelling
Hardening	Induration/hardening
Pain on touch	Pain/ tenderness (Pain on pressure)
Pain without touch	Pain (spontaneous / pain without pressure)
Itching	Pruritis/ itching
Burning	Burning sensation
Lump	Lump

Subject assessed individual injection site reaction examination results will be listed.

### 12.6.3 Laboratory Data

Descriptive statistics for clinical laboratory values (in SI units) and changes from baseline at each assessment time point will be presented by treatment group for the following clinical laboratory variables in [Table 6](#).

**Table 6: Clinical laboratory safety test analytes to be presented in summary tables**

Panel	Parameters	
Haematology	White blood cells (leukocytes)	Neutrophils [a]
	Red blood cells (erythrocytes)	Lymphocytes [a]
	Haemoglobin	Monocytes [a]
	Haematocrit	Eosinophils [a]
	Mean corpuscular volume	Basophils [a]
	Mean corpuscular haemoglobin	Platelets
	Mean corpuscular haemoglobin concentration	
Serum biochemistry	Sodium	Aspartate transaminase (AST)
	Potassium	Alkaline phosphatase (ALP)[b]
	Urea	Alanine aminotransferase (ALT)
	Creatinine	Creatine kinase [c]
	Albumin	Gamma-glutamyl transferase (gamma glutamyl transpeptidase) (GGT)
	Calcium	Lactate dehydrogenase
	Phosphate	Total and direct bilirubin
	Glucose	
	Total protein	
	C-reactive protein	
Coagulation	International normalised ratio of prothrombin time (INR)	
Urinalysis	Protein	Leukocyte esterase
	Bilirubin	Red blood cells
	Urobilinogen	pH
	Ketones	Nitrites
	Glucose	Specific gravity

[a] Given as both absolute count and as a percentage of total leukocyte count. In cases where only absolute counts or percentages of these leukocyte subtypes are recorded, the missing percentage or absolute count will be derived.

[b] Alkaline phosphatase iso-enzymes (liver-specific and bile duct specific) will be measured if original alkaline phosphatase test result is above the upper limit of normal.

[c] Creatine kinase MB or Troponin T will be measured where clinically indicated.

In addition, if protein and/or blood is/are detected during urinalysis then a microscopic examination will be conducted consisting of leukocytes, erythrocytes, casts and bacteria.

Laboratory results will be categorised as low, normal or high in relation to the local laboratory reference range, and shift tables from baseline to each time point will be presented.

Clinical laboratory test values are assessed for clinical significance by the investigator. The number and percentage of subjects with post-baseline clinically significant values will be tabulated by treatment group. The percentages will be calculated relative to the number of subjects with at least 1 post-baseline assessment.

All laboratory results will be listed, including microscopic urinalysis results if collected.

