- Bloods for assessing liver function will be taken at 7 days after each injection and prior to the subsequent injection. These results will be reviewed by the Principal Investigator (PI) for each site. Any subject experiencing an increase in alanine aminotransferase (ALT) to 10 times the upper limit of normal (ULN), a prothrombin time, reported as the international normalised ratio (INR) of more than 1.3 or a total bilirubin greater than 3 times the ULN, will be called back to study site for assessment and will not receive any more doses of Vaccine FP-02.2. Subjects with an ALT above 5 times the ULN will be closely monitored and dosed at the discretion of the Investigator.
- Any subject experiencing a flare with decreased liver function will be managed by the PI for the site, as per local clinical protocols.
- A safety review committee (SRC) (defined as the country CIs, if applicable, and the study medical monitors) will review and assess all safety data for Cohorts 1 and 2 after at least 15 or 30 subjects, respectively, have completed Day 36 assessments.

Communication between the sites to discuss subject safety is of critical importance and, in addition to the SRC. Sites are encouraged to contact the Sponsor's medical monitor or regional CIs for any questions or concerns about the study, especially if related to patient safety.

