7.6.1.2 Safety laboratory tests

Safety laboratory tests will be performed at the times indicated in the flow chart **Error! Reference source not found.** (see **Error! Reference source not found.** Table 1 Flow chart. At the screening visit the subjects will be screened for alcohol and drugs of abuse and infection with HIV, HDV and HCV. Further details are provided in Section 7.11.1.

The Investigator must review the laboratory report and document this review by signing the laboratory report form. Any clinically relevant values or changes in laboratory test values, as assessed against the normal reference ranges, must be recorded in the AE section of the subject's eCRF.

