7.10.1 Possible reasons for discontinuing subjects from continued study treatment

Examples of possible reasons for premature withdrawal of subjects:

- Major protocol violations;
- Pregnancy;
- Serious intercurrent illness;
- AEs which, in the judgement of the PI or Co-Investigator and subject to discussion with the Sponsor's medical advisor, justifies discontinuation;
- Non-compliance with study requirements;
- Withdrawal of consent by the subject;
- Subjects experiencing clinically significant injection site reactions or clinically significant changes in haematology and serum biochemistry results, considered possibly related to administration of the IMP, after a dose may not receive the subsequent dose of medication, at the discretion of the PI, in discussion with the Chief Investigator (CI) or the Sponsor's medical advisor. However, safety, virology and immunogenicity data will continue to be collected until the end of the study unless the subject withdraws his/her consent.

If a subject is withdrawn from study treatment, relevant study procedures e.g. physical examination, clinical laboratory analyses for safety and immunogenicity will be performed wherever possible. The reason(s) for discontinuation will be recorded in the appropriate section of the eCRF. Any subject who prematurely terminates participation and who has received at least one injection of the study treatment will undergo relevant post-study procedures for reasons of medical prudence, including a final examination and safety laboratory studies, unless the subject has withdrawn his/her consent and refuses to be examined and/or have blood drawn.

If a subject terminates participation due to an AE possibly related to the study medication or study procedures, the subject should be followed up by additional examinations according to the medical judgment of the Investigator until the abnormal condition is resolved or the Investigator deems further observations or examinations to be no longer medically indicated. If the subject refuses to be followed up the Investigator should explain the importance of the follow-up and encourage the subject to allow follow up. Subjects who elect to discontinue dosing should be encouraged to continue with other study procedures until the end of study if they are willing.

Study stopping rules

Individual subjects

An individual subject will have treatment discontinued if he/she experiences any one or more of the following events:

- ALT \geq 10 times the ULN

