- INR $>$ 1.3
- Total bilirubin >3 times the ULN

Study as a whole

Dosing will be stopped for all subjects and enrolment discontinued if 20% or more of subjects experience one or more of the following events

- ALT \geq 10 times the ULN
- INR $>$ 1.3
- Total bilirubin >3 times the ULN
- Serious adverse events considered related to investigational products

- Severe systemic reactions.

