7.11.1 Safety laboratory

Blood and urine samples will be collected for safety laboratory tests and screening for alcohol, drugs of abuse and HIV, HDV and HCV infection at the times indicated in the flow chart (see Table 1 Flow chart). The analytes listed in Table 5 will be determined.

Clinical laboratory tests (see Table 5) will be performed at local site hospital laboratories. Procedures for sample collection, processing, and storage will be described in a separate laboratory manual. Additional and repeat testing may be performed at the discretion of the Investigator.

Table 5 Clinical laboratory safety test analytes

Panel	Parameters	
Haematology	White blood cells (leukocytes)	Neutrophils [a]
	Red blood cells (erythrocytes)	Lymphocytes [a]
	Haemoglobin	Monocytes [a]
	Haematocrit	Eosinophils [a]
	Mean corpuscular volume	Basophils [a]
	Mean corpuscular haemoglobin	Platelets
	Mean corpuscular haemoglobin concentration	
Serum biochemistry	Sodium	Aspartate transaminase (AST)
	Potassium	Alkaline phosphatase (ALP) [b]
	Urea	Alanine aminotransferase (ALT)
	Creatinine	Creatine kinase [c]
	Albumin	Gamma-glutamyl transferase (gamma glutamyl transpeptidase) (GGT)
	Calcium	Lactate dehydrogenase
	Phosphate	Total and direct bilirubin
	Glucose	
	Total protein	
	C-reactive protein	
Coagulation	International normalized ratio of prothrombin time (INR)	
Urinalysis	Protein	Leukocyte esterase
	Bilirubin	Red blood cells
	Urobilinogen	pH
	Ketones	Nitrites
	Glucose	Specific gravity
Urine microscopy [d]	Microscopy to be performed if clinically indicated (as per local procedures)	
Viral serology [d]	Human immunodeficiency virus (HIV I and II)	Hepatitis C virus (HCV) antibodies
		Hepatitis D virus (HDV) antibodies
Drugs of abuse and alcohol screen [d]	Amphetamine/ecstasy	Opiates
	Ethanol	Benzodiazepines
	Cannabinoids	Methadone metabolites
	Cocaine	Barbiturates
	Urine creatinine	
Serum/urine pregnancy test [e]	Beta human chorionic gonadotropin	

[a] Given as both absolute count and as a percentage of total leukocyte count.

[b] Alkaline phosphatase iso-enzymes (liver-specific and bile duct specific) will be measured if original alkaline phosphatase test result is above the upper limit of normal.

[c] Creatine kinase MB or Troponin T will be measured where clinically indicated.

[d] At Screening Visit only.

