10.9.1 Liver function

Liver function test results will be presented using the standard summary statistics and shift tables.

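### No SAP table counts subjects by arm against the protocol's own liver limits, and off-schedule peaks may drop out of the summary counts

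*SAP*

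**What the plan says.** **Limits.** Protocol 2.1.4 has a lower ALT level: "Subjects with an ALT above 5 times the ULN will be closely monitored". For ALT at 10x ULN, INR above 1.3 or total bilirubin above 3x ULN, the subject "will be called back to study site for assessment" and gets no further vaccine. Protocol 7.10.1 repeats these three as individual stopping rules: "An individual subject will have treatment discontinued if he/she experiences any one or more of the following events", with ALT at or above 10x ULN, INR above 1.3 and "Total bilirubin >3 times the ULN" as the list.

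**Planned analysis.** Protocol 10.9.1: "Liver function test results will be presented using the standard summary statistics and shift tables". SAP 12.6.3 provides statistics and changes from baseline by time point in SI units, and shift tables by local reference range: "Laboratory results will be categorised as low, normal or high in relation to the local laboratory reference range". It adds a by-arm count of post-baseline values that the investigator judged clinically significant. All laboratory results are listed.

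**Off-schedule results.** Protocol 7.11.1: "Additional and repeat testing may be performed at the discretion of the Investigator". SAP 8.3 keeps data from unscheduled or repeated visits out of summary tables, apart from their use in deriving baseline. SAP 12.6 shows unscheduled visits in listings only. A repeat for a damaged sample is the exception: SAP 8.3 maps it to the scheduled visit.

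**Summary statistics.** Protocol 10.3 adds the geometric mean and coefficient of variation for positively skewed variables and gives liver enzymes as an example. SAP 12.0 lists n, mean, SD, median, quartiles, minimum and maximum. SAP 4.1 declares two changes from the protocol, and this is not one of them.

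**The concern.** Safety is the primary objective, and SAP 7.1 makes laboratory assessment of liver inflammation and function a primary variable. Protocol 2.1.4 names a flare with hepatic decompensation as a theoretical risk of an effective product. SAP 10.2 says that the Day 85 analysis will inform the next study and confirm formulation and dose.

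A reader comparing six arms will want to know how many subjects in each reached the levels that the protocol itself treats as important. As planned, that number must be rebuilt from listings of about 60 subjects. The one laboratory table that could pick up an off-schedule peak, the clinically significant count, is covered by a general rule that appears to exclude such results.

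**Working it through.** The plan states no figure to reproduce: there is no hypothesis test and no formal sample size calculation. The check compares outputs with limits, with some supporting arithmetic.

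**1. Outputs against limits** (SAP 12.1, 12.3.1, 12.6.1, 12.6.3, Appendix 1)

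| Planned output | What classifies a subject | Applies the limits? | Takes unscheduled results? |
|---|---|---|---|
| By-visit statistics | Nothing; values in SI units | No | No |
| Shift tables | Low, normal or high | No | No |
| Clinically significant values | Investigator judgement | No | Unclear: 12.6.3 alone would allow it, 8.3 and 12.6 would not |
| AESIs | Medical review; hepatic flare has no numeric definition | No | Event-based |
| TEAE, discontinuation, exposure | Event report or doses given | No | Event-based |
| Laboratory listings | Individual values, no by-arm count | No | Yes |

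**2. Shift tables.** A value is high when value/ULN exceeds 1.
- 0.8x to 1.1x: normal to high. 0.8x to 10x: normal to high. Same cell.
- Inclusion criterion 6 (ALT or AST at or below 1.5x ULN) lets a subject enter already high. 1.4x to 1.45x is a 1.45/1.4 = 1.04-fold rise; 1.4x to 12x is 12/1.4 = 8.6-fold. Both read high to high.

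**3. By-visit maxima.** A maximum of M is M/ULN multiples, and the ULN is local. The documents give no ULN. Assuming local ULNs of 35 to 55 U/L, a maximum of 400 U/L is 400/35 = 11.4x or 400/55 = 7.3x, on either side of 10x. Maxima at two visits also do not show whether one subject or two are involved.

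**4. Timing.** Scheduled post-dose safety laboratory days (protocol flow chart) are 8, 29, 36, 57, 64, 85 and 225. The gaps are 21, 7, 21, 7, 21 and 140 days. A peak inside a gap can be recorded only on an unscheduled test. Up to Day 85 the longest gap is 21 days; the 140-day gap bears only on the Day 225 analysis.

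**5. Discontinuation as a proxy.** The last planned dose is Day 57. A limit first reached on Day 64, 85 or 225 (3 of 7 scheduled laboratory days) leaves no planned dose to stop. ALT between 5x and 10x ULN does not by itself require stopping.

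**6. INR.** SAP Table 6 lists INR for summary tables. Appendix 1 names 3 tables for each of haematology, biochemistry and urinalysis (3 x 3 = 9), and 3 matching listings plus pregnancy. None is named for coagulation.

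**7. Statistics.** Protocol 10.3 promises the geometric mean and coefficient of variation for liver enzymes. SAP 12.0 and 12.6.3 include neither, and SAP 4.1 does not mention the change.

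**8. What a count can show.** With 0 of 10 subjects at a limit, the exact two-sided 95% upper bound is 1 - 0.025^(1/10) = 30.8%. The counts would describe the arms; they would not rank them.

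**The case against.** The other side has much in its favour.

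- Protocol 10.9.1 asks for summary statistics and shift tables, and the SAP supplies both. A reader might infer that omitting a limit table breaches that section. It does not: neither document promises such a table. The departure that does exist is the missing geometric mean and coefficient of variation under protocol 10.3.
- Protocol 7.6.1.2 says "Any clinically relevant values or changes in laboratory test values, as assessed against the normal reference ranges, must be recorded in the AE section". Day 85 is 28 days after the scheduled last dose, inside the 30-day TEAE window, so most serious rises should reach a by-arm adverse event table. AESI, discontinuation and exposure tables add to this. After Day 85 only SAEs and AESIs are collected, but hepatic flares are AESIs. This stands and limits the size of the point. It does not supply the count, because none of these outputs applies the limits.
- A 12x value at a scheduled visit would show as a large maximum and a large maximum change. It would not be hidden. It could not be read reliably as a multiple of ULN.
- Recall under protocol 2.1.4 follows a result that has already reached a limit, so recall tests mostly affect the recorded peak. That is right for the limit that triggered the recall. A second limit could still first be met on a recall test, and any limit could first be met on a discretionary repeat.
- Worst-value counts favour finding events in subjects tested more often. This stands and shapes the fix. SAP 8.3 says that some subjects attended extra visits under earlier protocol versions. Cohort 1, as planned, holds all 10 Low-dose subjects but only 5 of the 10 placebo subjects. Whether those visits included laboratory tests is not stated.
- INR may be meant to sit under another panel's outputs. If so, a line in Appendix 1 settles it.

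**Conclusion.** The point holds as a minor reporting gap. No planned output counts subjects by arm against the protocol's liver limits, the shift tables cannot separate a slight rise from one past 10x ULN, and the rule on unscheduled results leaves it unclear whether an off-schedule peak enters even the clinically significant table. The undeclared loss of the geometric mean and coefficient of variation is a small departure from the protocol.

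Two stronger readings are not supported. One is that liver events would be lost: all results are listed, and clinically relevant values go to the adverse event section. The other is that subjects are less protected or that the study-level 20% rule cannot work. That rule and the individual limits are applied during the trial, the rule runs across all subjects, and data given to the Safety Review Committee are blinded. An end-of-study table by arm serves none of this.

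The conclusion rests on the text of the two documents. The ULN range of 35 to 55 U/L is an illustration only, and nothing depends on it.

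**What to change.** 1. Add one by-arm table on the Safety Analysis Set: worst post-baseline ALT and total bilirubin in multiples of the local ULN, and worst INR, with subjects counted against the existing protocol limits. Use all post-baseline values, including unscheduled ones. Split by baseline status, including INR already above 1.3, since no eligibility criterion limits INR. Show the number of tests per subject by arm, and beside it the same counts from scheduled visits alone, because testing frequency may differ by arm.
2. State in SAP 8.3 and 12.6 that this table and the clinically significant tables include unscheduled results. Leave the by-visit summaries as they are.
3. Name in Appendix 1 where INR is tabulated and listed.
4. Restore the geometric mean and coefficient of variation for liver enzymes, or declare the change in SAP 4.1.

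Cost: one table run at both analyses, a sentence in each of two SAP sections, a line or two in Appendix 1, and two added statistics or one declared change. The data are already collected, and the local reference ranges are already needed for the shift tables. The downside is uneven ascertainment, which the scheduled-only counts and tests per subject make visible but do not remove. With about 10 subjects per arm, the counts are descriptive only. No clinical limit changes.
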